### **6.10.2. Major Secondary Efficacy Analysis**

The major secondary outcomes are:

- To evaluate in patients having achieved a state of sustained remission whether ixekizumab 80 mg every 4 weeks (Q4W) treatment group is superior to placebo in maintaining response as measured by the proportion of patients in the randomized-withdrawal population who do not experience a flare during the randomized withdrawal-retreatment period
- To evaluate in patients having achieved a state of sustained remission whether the Combined Ixekizumab treatment group is superior to the placebo group in maintaining response after treatment withdrawal as measured by the time to the first flare during the randomized withdrawal-retreatment period
- To evaluate in patients having achieved a state of sustained remission whether the ixekizumab 80 mg Q4W treatment group is superior to placebo in maintaining response after treatment withdrawal as measured by the time to the first flare during the randomized withdrawal-retreatment period.

The primary analysis for categorical major secondary outcomes is a logistic regression analysis with treatment, geographic region, and originating study will be included in the model (Section 6.1.3.1). In the case when logistic regression model does not produce statistical results due to sparse data, Fisher's exact test will be used. Missing data will be imputed using the NRI method (Section 6.3.2).

Kaplan-Meier product limit method will be used to estimate the survival curves for time to the first flare for patients in RW ITT Population during Period 2. The number of patients at risk and experiencing flare by each scheduled visit during Period 2 will be presented by treatment group. The Kaplan-Meier estimate of the proportion of patients experiencing flare will be presented for each visit. Treatment group comparisons will be performed using the log-rank test with strata of geographic region and originating study. A Kaplan-Meier plot of time to the first flare by treatment group will also be provided. See Section 6.1.3 for censored data.

The variable derivations for the major secondary outcomes are described in [Table RHBY.6.4](#).

The treatment group comparisons for the primary and major secondary outcomes will be tested based on the graphical multiple testing procedure detailed in Section 6.5.

### **6.10.3. Additional Analyses of the Primary Outcome**

Unless otherwise specified, there will be no adjustment for multiple comparisons for additional analyses of the primary outcome, the occurrence of flare.

Figures showing the proportion of patients not experiencing a flare at each scheduled visit during Period 2 within each treatment group will be provided.

[Table RHBY.6.5](#) provides the detailed analyses including measurement, variables, analysis method and imputation, population, treatment group comparisons, and time points for primary and secondary efficacy analyses.

### **6.10.4. Other Secondary Efficacy Analyses**

There will be no adjustment for multiple comparisons for other secondary efficacy analyses.

[Table RHBY.6.5](#) provides the detailed analyses including measurement, variables, analysis method and imputation method, population, treatment group comparisons, and time points for primary and secondary efficacy analyses.

## **6.11. Health Outcomes/Quality-of-Life Analyses**

The health outcomes and quality of life (QOL) measures are ASAS HI, SF-36, EQ-5D-5L, Fatigue NRS, JSEQ, WPAI-SpA, and Quick Inventory of Depressive Symptomatology—Self Report 16 items (QIDS-SR16).

The analyses of health outcomes and QOL measures will be carried out for the RW ITT Population during Period 2 and for the Long-Term Ixekizumab Treatment Population during the Combined Periods 1 and 2, and Combined Periods 1, 2, and 3. There will be no adjustment for multiple comparisons for RW ITT Population during Period 2.

[Table RHBY.6.6](#) includes the description and derivation of the health outcomes and QOL measures.

[Table RHBY.6.7](#) provides the detailed analyses including measurement, variables, analysis method and imputation method, population, treatment group comparisons, and time points for health outcomes and QOL analyses.

**Table RHBY.6.6. Description and Derivation of Health Outcomes and Quality-of-Life Measures**

Measure	Description	Variable	Derivation / Comment	Imputation Approach if with Missing Components
ASAS Health Index	The ASAS Health Index (ASAS HI) is a disease specific health-index instrument designed to assess the impact of interventions for SpA, including axSpA. The 17 item instrument has scores ranging from 0 (good Health) to 17 (poor Health) (Kiltz et al. 2015). Each item consists of 1 question that the patient needs to respond to with either “I agree” (score 1) or “I do not agree (score 0).” A score of “1” is given where the item is affirmed, indicating adverse health.	ASAS-HI	All item scores are summed to give a total score or index. Range: 0 to 17 0 (good health) and 17 (poor health) Note: items # 7 and #8 are not applicable for all patients. Item with response of ‘not applicable’ is considered as missing item.	If ≥4 items (>20%) have missing response, then ASAS-HI is missing. If <4 items (≤20%) missing, then imputed sum = sum of scores from nonmissing items × 17/ (17- no. of missing items). If answer to item #7 or #8 is NA, it is considered as missing (ie, if responses to both #7 and #8 are not applicable, then then patient can only have 1 more missing response for the total score to be calculated. [ASAS Health Index User Manual (WWW)].
			Change from baseline in ASAS-HI	Calculated as: observed ASAS-HI – baseline ASAS-HI Missing if baseline or observed value is missing
Medical Outcomes Study 36-item Short-Form Health Survey	The SF-36 is a 36-item patient-administered measure designed to be a short, multipurpose assessment of health in the areas of physical functioning, role – physical, role – emotional, bodily pain, vitality, social functioning, mental health, and general health. The 2 overarching domains of mental well-being and physical well-being are captured by the Mental Component Summary and Physical Component Summary scores. The higher scores indicate better levels of function and/or better health. Items are	8 associated domain scores (scaled score and t-score): 

• Physical Functioning,

• Role Physical,

• Bodily Pain,

• General Health,

• Vitality,

• Social Functioning,

• Role Emotional,

• Mental Health

	Per copyright owner, the Quality Metric Health Outcomes™ Scoring Software will be used to derive SF-36 domain and component scores. After data quality-controls, the SF-36 software will re-calibrate the item-level responses for calculation of the domain and component scores. These raw scores will be transformed into the domain scores (t-scores) using the 1-week recall period. The procedure to derive the SF-36 scores is described in Appendix 4 . It entails exporting the patient data in a CSV or tab-delimited file for import, generation of the	If an item is missing, there will be imputation conducted by the Scoring Software.

Measure	Description	Variable	Derivation / Comment	Imputation Approach if with Missing Components
	answered on Likert scales of varying lengths. The SF-36 version 2 (acute version) will be used, which utilizes a 1-week recall period (Ware [2000]).	2 component Scores (t-score): 
 
• MCS Score
 
• PCS Score
 
	SF-36 scores and reports, and export of the calculated scores in a CSV or tab-delimited file for integration into SDTM/ADaM datasets. .	
		change from baseline in PCS, MCS and domain scores	Calculated as: observed score – baseline score	Missing if baseline or observed value is missing
Fatigue Severity Numeric Rating Scale	The fatigue severity NRS is a patient-administered single-item 11-point horizontal scale anchored at 0 and 10, with 0 representing “no fatigue” and 10 representing “as bad as you can imagine” (Naegeli et al. 2013). Patients rate their fatigue (feeling tired or worn out) by circling the 1 number that describes their worst level of fatigue during the previous 24 hours.	Fatigue Severity NRS	Range: 0 to 10. 0 (no fatigue) and 10 (as bad as you can imagine).	Single item, missing if missing
		change from baseline in Fatigue Severity NRS	Calculated as: observed score – baseline score	Missing if baseline or observed value is missing
		Fatigue Severity % improvement from baseline	Calculated as: $\frac{\text{Percent improvement from baseline}}{100} = \frac{\text{Baseline score} - \text{Observed score}}{\text{Baseline score}}$	Missing if baseline or observed value is missing
Work Productivity and Activity Impairment Questionnaire—Spondyloarthritis	The Work Productivity Activity Impairment—Spondyloarthritis (WPAI-SpA) consists of 6 questions to determine: 1. employment status; 2. hours missed from work because of spondyloarthritis; 3. hours missed from work for other reasons; 4. hours actually worked; 5. the degree to which spondyloarthritis affected work productivity while at work; 6. the degree to which spondyloarthritis affected activities outside of work. The WPAI-SpA has been validated in the	percentage of absenteeism	% work time missed due to problem: $(Q2/(Q2 + Q4)) * 100$	if Q2 or Q4 is missing, then missing
		change from baseline in percentage of absenteeism	Calculated as: observed value – baseline value	if baseline or observed value is missing, then missing
		percentage of presenteeism	% impairment while working due to problem: $(Q5/10) * 100$	if Q5 is missing, then missing
		change from baseline in percentage of presenteeism	Calculated as: observed value – baseline value	if baseline or observed value is missing, then missing
		overall work impairment (work productivity) score	% overall work impairment due to problem: $(Q2/(Q2 + Q4) + [(1 - Q2/(Q2 + Q4)) * (Q5/10)]) * 100$	if any of Q2, Q4, or Q5 is missing, then missing

Measure	Description	Variable	Derivation / Comment	Imputation Approach if with Missing Components
	rad-axSpA patient population (Reilly et al. 2010). Four scores are derived: percentage of absenteeism, percentage of presenteeism (reduced productivity while at work), an overall work impairment score that combines absenteeism and presenteeism, and percentage of impairment in activities performed outside of work. Greater scores indicate greater impairment (Reilly Associates Health Outcomes Research [WWW]).	change from baseline in overall work impairment score	Calculated as: observed value – baseline value	if baseline or observed value is missing, then missing
		percentage of activity impairment	% activity impairment due to problem: $(Q6/10)*100$	if Q6 is missing, then missing
		change from baseline in percentage of activity impairment	Change from baseline is calculated as: observed value – baseline value	if baseline or observed value is missing, then missing
Jenkins Sleep Questionnaire	The Jenkins Sleep Evaluation Questionnaire (JSEQ) is a 4 item scale designed to estimate sleep problems in clinical research. The JSEQ assesses the frequency of sleep disturbance in 4 categories: 1) trouble falling asleep, 2) waking up several times during the night, 3) having trouble staying asleep (including waking up far too early), and 4) waking up after the usual amount of sleep feeling tired and worn out. Patients report the numbers of days they experience each of these problems in the past month on a 6-point Likert Scale ranging from 0 = “no days” to 5 = “22-30 days.”	JSEQ score	Sum of 4-item score (each on a 6-point Likert scale, 0 = no days and 5 = 22-30 days). Range: 0 to 20, higher scores indicating greater sleep disturbance (Deodhar et al. 2010)	Missing if >20% items (ie, any of the 4) are missing
		change from baseline and % improvement from baseline in JSEQ score	Change from baseline calculated as: observed JSEQ – baseline JSEQ  Percent improvement from baseline $= 100 \times \frac{\text{Baseline score} - \text{Observed score}}{\text{Baseline score}}$	Missing if baseline or observed value is missing
Quick Inventory of Depressive Symptomatology-self	See Section 6.13.6 for description of QIDS-SR16	9 Domains	See Section 6.13.6 for description of each domain	See Section 6.13.6
		Change from baseline in each domain	Calculated as: observed domain score – baseline domain score	Missing if baseline or observed value is missing

Measure	Description	Variable	Derivation / Comment	Imputation Approach if with Missing Components
report 16 items		16 Individual items	Range: 0 to 3.	Missing if the item is missing.
		Change from baseline in each individual item	Calculated as: observed individual item score – baseline individual item score	Missing if baseline or observed value is missing
		QIDS-SR16 total score	See Section 6.13.6 for description of QIDS-SR16 total score	See Section 6.13.6
		Change from baseline in QIDS-SR16 total score	Calculated as: observed total score – baseline total score	Missing if baseline or observed value is missing
		Proportion of patients with at least a 50% decrease in QIDS-SR16 total score	% reduction from baseline calculated as: $100 \times \frac{\text{Baseline} - \text{Observed score}}{\text{Baseline}}$ If the value of % reduction from baseline is $\geq 50$ , patients had at least a 50% decrease in QIDS-SR16 total score.	Missing if baseline or observed score is missing
European Quality of Life – 5 Dimensions 5 Level	
EQ-5D-5L: is a standardized measure of health status used to provide a simple, generic measure of health for clinical and economic appraisal. The EQ-5D-5L consists of 2 components: a descriptive system of the respondent's health and a rating of his/her current health state using a 0- to 100-mm VAS. The descriptive system comprises the following 5 dimensions:
 
 
item 1: mobility
 
item 2: self-care
 
item 3: usual activities
 
item 4: pain/discomfort
 
item 5: anxiety/depression
 
 
The respondent is asked to indicate
	
EQ-5D mobility, EQ-5D self-care, EQ-5D usual activities, EQ-5D pain/discomfort, EQ-5D anxiety/depression
 
EQ-5D-5L UK Population-based index score
	
Five health profile dimensions, each dimension has 5 levels:
 
 
1 = no problems
 
2 = slight problems
 
3 = moderate problems
 
4 = severe problems
 
5 = extreme problems
 
 
It should be noted that the numerals 1 to 5 have no arithmetic properties and should not be used as a primary score.
	
Each dimension is a single item, missing if missing.
 
If any of the items is missing, the index score is missing

Measure	Description	Variable	Derivation / Comment	Imputation Approach if with Missing Components
	his/her health state by ticking (or placing a cross) in the box associated with the most appropriate statement in each of the 5 dimensions.		produce a patient-level index score between -0.59 and 1.0 (continuous variable): http://www.euroqol.org/fileadmin/user_upload/Documenten/Excel/Crosswalk_5L/EQ-5D-5L_Crosswalk_Value_Sets.xls	
	The VAS records the respondent's self-rated health on a vertical VAS where the endpoints are labeled 100 = "best imaginable health state" and 0 = "worst imaginable health state".	EQ-5D VAS	Range from 0 = "worst imaginable health state" to 100 = "best imaginable health state". Note: higher value indicates better health state.	Single item, missing if missing

Abbreviations: Baseline = baseline from the originating study RHBV, RHBW or RHBX; EQ-5D-5L = European Quality of Life – 5 Dimensions 5 Level; MCS = mental component summary; NRS = numeric rating scale; SF-36 = Medical Outcomes Study 36-Item Short-Form Health Survey; PCS = physical component summary; UK = United Kingdom; VAS = visual analog scale.

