9.1.2.15.6. Work Productivity and Activity Impairment Questionnaire—Spondyloarthritis

The Work Productivity Activity Impairment Questionnaire-Spondyloarthritis (WPAI-SpA) consists of 6 questions to determine employment status, hours missed from work because of spondyloarthritis, hours missed from work for other reasons, hours actually worked, the degree to which spondyloarthritis affected work productivity while at work, and the degree to which spondyloarthritis affected activities outside of work. The WPAI-SpA has been validated in the rad-axSpA patient population (Reilly et al. 2010). Four scores are derived: percentage of absenteeism, percentage of presenteeism (reduced productivity while at work), an overall work impairment score that combines absenteeism and presenteeism, and percentage of impairment in activities performed outside of work. Greater scores indicate greater impairment (Reilly Associates Health Outcomes Research [WWW]).

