### 6.3.3. Modified Baseline Observation Carried Forward

An mBOCF imputation will be performed on continuous efficacy and health outcome variables. For patients discontinuing study drug due to an AE, the baseline observation at Week 0 in originating study will be carried forward to the corresponding time point for evaluation. For patients discontinuing study drug for any other reason, the last nonmissing observation before discontinuation will be carried forward to the corresponding time point for evaluation. For patients who discontinue originally assigned blinded study treatment and were retreated due to flare, or patients who are escalated from ixekizumab 80 mg Q4W to ixekizumab 80 mg Q2W, the last nonmissing observation prior to the retreatment or escalation will be carried forward to subsequent time points. For intermittent missing data before the discontinuing study drug due to any reason, the last nonmissing observation (including observation at Week 24) before the intermittent missing data will be carried forward. Randomized patients at Week 24 without at least 1 postrandomization observation will not be included for evaluation for RW ITT Population, with the exception of patients discontinuing study treatment because of an AE, including death.

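### The WPAI-SpA overall work impairment score is set to missing when Q5 is missing, even for a patient wholly off work through the disease, whose score the SAP's formula already fixes at 100%

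*SAP*

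**What the plan says.** SAP Table RHBY.6.6 describes Q2 as "hours missed from work because of spondyloarthritis", Q4 as "hours actually worked", and Q5, in the same words as Protocol Section 9.1.2.15.6, as "the degree to which spondyloarthritis affected work productivity while at work". Apart from its opening bracket, the overall score is "Q2/(Q2 + Q4) + [(1 - Q2/(Q2 + Q4)) * (Q5/10)]) * 100". Higher scores are worse.

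The missing-data rules in the same table differ by score:

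- Absenteeism, which uses only Q2 and Q4: "if Q2 or Q4 is missing, then missing".
- Overall work impairment: "if any of Q2, Q4, or Q5 is missing, then missing". There is no exception for a patient who worked no hours.
- Change in overall work impairment: "if baseline or observed value is missing, then missing".

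SAP Table RHBY.6.7 analyses WPAI-SpA in Period 2 by ANCOVA with mBOCF in the RW ITT population. The long-term population is described using mBOCF and MMRM. For an intermittent gap, SAP Section 6.3.3 states that "the last nonmissing observation (including observation at Week 24) before the intermittent missing data will be carried forward". A randomized patient with no postrandomization value is left out, unless study drug was stopped for an adverse event.

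**The concern.** A score can be fully determined by answers that were collected and still be discarded because a question that cannot affect it was left blank. The blank is most likely when work impairment is at its maximum, so the loss is informative. Nothing in the Period 2 analysis restores the value. mBOCF replaces it with an earlier score, and in Group B that may be one taken at Week 24, shortly after the patient qualified on the remission criteria.

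The rule can also leave an inconsistent record. Under the SAP's formula the overall score is never below absenteeism, because the Q5 term only adds to it. Yet the analysis data could hold absenteeism of 100% next to a carried-forward overall score of, say, 10%.

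What is at stake is one of the four WPAI-SpA scores, an other secondary health outcome without multiplicity adjustment.

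**Working it through.** The plan states no figure on this point to reproduce. The check evaluates the SAP's formula and then applies its missing-data rules.

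**Formula.** Let A = Q2/(Q2+Q4). Overall score = 100 x [A + (1 - A) x Q5/10].

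**Step 1: patient wholly off work because of the disease (Q2>0, Q4=0).** A = Q2/(Q2+0) = 1, so the score = 100 x [1 + 0 x Q5/10] = 100. Evaluating Q2 = 1, 8, 20, 37.5, 40 and 60 with each Q5 from 0 to 10 gave 100 every time. Absenteeism for the same patient is 100 x 40/(40+0) = 100%, taking Q2 = 40.

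**Step 2: bound on a carried value.** No score can exceed 100. If some hours were worked, the score is below 100 unless Q5 = 10. A carried value is therefore better than the lost one or at most equal to it.

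**Step 3: illustration with assumed answers.**

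| Visit | Q2 | Q4 | Q5 | Score by formula | Score under current rule |
|---|---|---|---|---|---|
| Originating baseline | 8 | 32 | 5 | 100 x [0.2 + 0.8 x 0.5] = 60 | 60 |
| Week 24 | 0 | 40 | 1 | 100 x [0 + 1 x 0.1] = 10 | 10 |
| Week 40 | 40 | 0 | blank | 100 | missing; 10 carried forward |

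Change at Week 40 under the current rule: 10 - 60 = -50, an improvement. By the formula: 100 - 60 = +40, a worsening. The two differ by 90 points for this one patient.

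**Step 4: loss at the originating baseline.** The change-score rule then makes every later change missing for that patient. Under SAP Section 6.1.3.1 the baseline value is also a covariate in the Period 2 ANCOVA.

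**Step 5: effect on an arm mean.** If a share f of the analysed patients in an arm is affected at a visit and the carried value averages c, the mean is understated by f x (100 - c). The documents give neither f nor c, so both are assumed:

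| f | c = 80 | c = 50 | c = 30 | c = 10 |
|---|---|---|---|---|
| 1% | 0.2 | 0.5 | 0.7 | 0.9 |
| 2% | 0.4 | 1.0 | 1.4 | 1.8 |
| 5% | 1.0 | 2.5 | 3.5 | 4.5 |
| 10% | 2.0 | 5.0 | 7.0 | 9.0 |

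The shift in the treatment difference is the gap between the two arms' values of f x (100 - c). It is zero if the arms are equally affected.

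**The case against.** **The blank Q5 is not documented.** Protocol and SAP paraphrase the six questions. They show no skip instruction and do not say whether the ePRO tablet (Protocol Appendix 3.2.1) lets an item be passed over. A patient who answers Q5 anyway scores 100 and nothing is lost. This stands, so the blank must be put as likely from the wording and not as certain.

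**Few patients can be affected in Period 2.** Group B is seen every four weeks and retreated on flare. Under SAP Sections 6.1.3.1 and 6.3.3, data after retreatment are replaced by the last earlier value whatever the WPAI rule says, and the planning assumption is a 70% flare rate on placebo. As far as the Schedule of Activities columns can be read, WPAI-SpA is collected after randomization in Period 2 only at Week 40 and around Week 64, plus any early termination visit. An affected patient must be employed, wholly off work and not yet retreated at one of these visits. This stands and limits the effect.

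**The work loss stays visible.** Absenteeism and activity impairment do not need Q5 and are analysed too. True, but it does not make the overall score right.

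**The long-term analysis also uses MMRM,** which carries nothing forward. A lost baseline still removes the patient from the change analysis, and the missingness still depends on the unrecorded value. SAP Section 6.3.4 describes component-level multiple imputation for long-term continuous variables, and any imputed Q5 would return 100 here. But Table RHBY.6.7 does not list that method for WPAI-SpA, and it does not reach Period 2.

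**A reader might infer that the rule biases ixekizumab versus placebo toward no difference.** The documents do not support that as a general statement. It follows only if placebo has proportionately more such patients, which is plausible after withdrawal but not given. Similarly, long-term improvement is understated by excluding patients off work at baseline only if they improve more than the rest.

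**Conclusion.** The point holds as a minor defect in a stated derivation rule. The algebra is exact and rests on no assumption: with Q2>0 and Q4=0, Q5 carries no information, yet its absence deletes a score of 100%.

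That this happens in practice rests on Q5 being left blank by patients who worked no hours. The size rests wholly on assumed f and c. Over the range shown, the understatement of an arm mean runs from 0.2 points (f=1%, c=80) to 9.0 points (f=10%, c=10), and retreatment and sparse visits make the lower part more likely in Period 2. The direction of any between-arm bias is not established.

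The primary and major secondary outcomes use flare and time to flare, so they are unaffected. It would be wrong to read this as a threat to the trial's main conclusions.

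**What to change.** Replace the missing-data rule for the overall score in SAP Table RHBY.6.6 with:

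> If Q2>0 and Q4=0, overall work impairment = 100 irrespective of Q5; otherwise missing if any of Q2, Q4 or Q5 is missing, or if Q2+Q4=0.

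The last clause is needed because Q2 = Q4 = 0 leaves the formula undefined (0/0). Apply the rule at all visits, including the originating-study baseline. Leave presenteeism missing when Q5 is missing, since it has no meaning for a patient who did no work.

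The cost is one line of SAP text, the matching derivation code, and re-derivation of the baseline scores from the three originating studies, whose own WPAI rules are not in these documents. No new data are needed. The change only evaluates the SAP's existing formula, so a patient who answered Q5 keeps the same score.
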